10.0 Treatment

Bright IDEAS Adult Cancer (Bright IDEAS-AC): The PSST intervention will be delivered in the most patient-friendly way. Sessions 1 and 8 (S1, S8) will be face-to-face at the location of patient choice (hospital, clinic, or participant's home). The rest of the sessions (S2-7) will be delivered over the phone by research assistants (RAs) who have received training in PSST skills building and supervision. Before enrollment, each participating cancer survivor will receive a description of the Bright IDEAS-AC intervention, associated goals, and the randomization procedure in an informed consent document. All sessions will be audiotaped for quality assurance

Care As Usual Group (CAU): Participants randomized to the CAU group will be observed under naturalistic conditions. Both PSST and CAU participants and their clinicians (PCP and oncology providers) will be allowed to use any clinically appropriate medical and behavioral care without restriction (e.g., care management, rehabilitation, behavioral therapy, palliative care) or refer patients to social and community services (e.g., peer support, county cancer services program or aging services). The CAU participants will undergo the same evaluation protocol as the PSST group. After study completion, the CAU participants will be offered the PSST training manuals.

11.0 Procedures Involved

The Months 1-6 of the project is the adaptation phase. Using the NCI Guidelines for Choosing and Adapting RTIPs^{1,2} and RE-AIM framework for implementation and dissemination, we will start by revising the program materials and training protocol to adapt them for the needs of cancer survivors and their caregivers. While the basic principles and approaches of PSST are generalized to a wide range of health and non-health related situations (e.g., providing at home care-giving to a disabled spouse, waiting for a refugee status after being displaced from your home county during a civil war crisis), using relevant examples will accelerate learning and improve information retention and new skills development. Based on the analysis of CRC survivorship literature and qualitative interviews with community oncology providers (VROC preliminary data), we have identified five most common clinical problems that affect cancer survivors and five social issues that all cancer survivors have a hard time dealing with (Table 1). Working together, the project team will review the Bright IDEAS materials to identify areas (processes, timing or examples) that are unique for mothers of pediatric cancer patients but not relevant for adult cancer survivors and their caregivers (ex., prioritizing between the care for the sick child and the needs of his healthy siblings). Using the experience and expertise of the project team, we will adapt these materials to reflect specific challenges that cancer survivors are likely to experience and/or have difficulty addressing. Once all revisions are completed, the updated manuals and materials will be piloted with 5 adult cancer survivors and their caregivers. Their feedback will be reviewed by the study team and incorporated in the study documents. The revised materials will be then pilot-tested with 5 adult cancer survivors and caregivers from WCI. The study team will review the results of the pilot test and make any necessary changes to the study approach.

The study recruitment will start in Month 7 and continue for 10 months with last patient completing the follow-up by Month 23 (Figure 2). To ensure that men and women are adequately represented in the study sample, study randomization will be stratified by sex. In this study, we will pay close attention to the impact of patient sex and gender on their unmet needs and self-reported issues (for

Roswell Park Protocol Number. I 65518

instance, female cancer survivors may be less comfortable discussing their bowel issues and body image with their male partners and prefer to use a sister or a female friend as a caregiver). Based on the results of the study, we may develop a differential recruitment and/or training strategy for the future multisite study. For instance, if we find out that male cancer survivors are more likely to drop out of therapy or prefer face-to-face therapy (vs. over the phone), we will take that into account when designing the intervention for the larger pragmatic study.

The survivorship program coordinator (WCI - patients at all locations) and colorectal clinic nurse manager (RPCI patients) together with RAs will identify adult cancer patients who have completed adjuvant treatment for stage I-III cancer and who are eligible for survivorship consultation. Two weeks before the scheduled survivorship appointment, the survivorship nurse/CRC nurse manager will send the patient a study letter followed by a phone call, telling them about the study goals and procedures (e.g., duration of assessment and frequency of follow-up) and inviting them to participate. Patients who express interest will meet with the study RA in the location of their choice (hospital, clinic or patient home).

To determine patient eligibility, patients will be screened for cancer-related distress using the NCCN Distress Thermometer (Appendix 2). Patients who are experiencing psychological distress (NCCN Distress >2 cut-off has 100% sensitivity),⁶² and who meet the study's other inclusion and exclusion criteria (see below) will be invited to participate (patient with the distress level 4 or greater will be referred to therapy). If a person is willing to continue the screening process by providing written informed consent, he or she will then be asked to complete their baseline evaluation consisting of a battery of self-report measures (Table 2). The cancer patient will also be asked to identify a Supportive Other (SO) who might serve as a problem-solving partner. Inclusion and exclusion criteria: To be eligible to participate in this study, individuals will need to (a) meet the screening criteria for psychological distress (NCCN Distress >2 , PROMIS Anxiety >50 or any other clinical measure of mild distress); (b) be able to speak English; (c) have a 5-year survival rate of 50% or greater as deemed by their oncologist, surgeon, or other relevant attending physician (suggesting a reasonable rate of cure or prolonged medical survival with state-of-the-art medical care); and (d) be willing to provide written informed consent to participate in the study which includes several clinical evaluations, provide access to medical records/PCP, and allow all interviews and PSST therapy sessions to be audiotaped. Exclusion criteria include the presence of (a) a diagnosis of mental retardation, and/or (b) acute suicidal behavior. Among patients treated in the urban centers, we will specifically target patients who live more than 40 miles away from the clinic as they are more likely to experience problems with access to care. All study procedures and materials will be reviewed and approved by the Institutional Review Board to ensure maximum protection of patient privacy and confidentiality, HIPAA compliance, and appropriate data handling (see Data and Safety Monitoring Plan). Sample size justification: Based on the participating sites enrollment history, we expect an average enrollment rate of 3 new cancer survivors a month at WCI, 2 from RPCI, and 1 new cancer survivor every other month at NMH for 10 months (Figure 2). We will stop enrollments once we achieve 50 participants.

The RAs will collect patient self-reported demographic, clinical, and socio-economic information at the baseline (age, gender, race/ethnicity, employment status, education, health insurance, place of residence, living arrangements, diagnosis, SCP or treatment history and time since diagnosis and end of treatment) as well as the information about the SO (age, sex, education level, religion/ethnicity, racial background, cancer history and relationship to the patient). We will collect data to help quantify the burden of enrollment process including duration of the initial

Roswell Park Protocol Number. I 65518

meeting between the patient and study coordinator and informal consent, number, duration and content of subsequent meetings and phone calls before and after patient/SO enrollment. At every stage, we will capture patient feedback and reasons for refusal to participate.

Caregivers are asked to play their usual supportive role and invited to participate in the therapy sessions and exercises, talk with patients about their problems, offer solutions and emotional support. They are also invited to participate in evaluations and qualitative interviews.

All patients in the intervention and control arms, as well as any participating caregivers, at the time of T0, T1, and T2 assessments will be asked about their healthcare utilization since the last assessment including primary care, specialist and ED visits and any hospital stays. This information will be validated with the patient SO and medical record/Primary Care Provider (PCP) office staff. For RPCI patients, information about number and timing of care visits will be requested electronically. For external patients, the RA will call the PCP office staff and confirm all patient-reported clinic visits after the medical record release form is signed. We will also ask about reasons for the visits to further distinguish utilization into avoidable (consequence of poor quality of care or insufficient self-management skills) and unavoidable (true healthcare emergency).

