H2: At least 80% of patients will complete 80% of PSST sessions after randomization.

H3: At least 50% of patients will identify the burden of PSST training as < 3 on a 5-item Likert scale.

[figure not shown]
H4: At least 50% of patients with cancer will identify a significant other to join them in PSST training.

H5: Strategies associated with higher levels of institutional feasibility and sustainability of Bright IDEAS-AC affect provider burden and teamwork and institutional resources and workflow.

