4.0 Local and Study-Wide Number of Subjects

4.1

Based on the participating sites enrollment history, we expect an average enrollment rate of 3 new survivors a month at Wilmot Cancer Institute (WCI), 2 from RPCI (up to 20), and 1 new survivor every other month at [name] Memorial Hospital (NMH), an offsite Wilmot Cancer Institute location, for 10 months. We will stop enrollments once we achieve 50 participants. We plan to recruit 50 patients and as many caregivers as possible.

4.2

One of the study goals is to estimate attrition rate for this protocol.

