8.0 Study Endpoints

8.1

We will collect data to help quantify the burden of enrollment process including duration of the initial meeting between the patient and study coordinator and informal consent, number, duration and content of subsequent meetings and phone calls before and after patient/SO enrollment. At every stage, we will capture patient feedback and reasons for refusal to participate.

Table 2: Study self-reported instruments and questionnaires administered at T0, T1, and T2*

Instrument	Short title	Number of items	Total score	Description
Social Problem-Solving Inventory-Revised^{32,33} (Appendix 5)	SPSI-R	52	0-20	±Problem Orientation, Rational Problem Solving, Impulsivity/ Carelessness Style, Avoidance Style
Patient Health Questionnaire-2³⁴ (Appendix 6)	PHQ-2	2	0-6	scoring each answer as 0 (“not at all”) to 3 (“nearly every day”)
Hospital Anxiety and Depression Scale^{35,36}(Appendix 7)	HADS	7+7	0-21	Depression/anxiety symptoms over the last week; scores >11 considered abnormal
The Functional Assessment of Cancer Therapy–disease specific³⁷(Appendix 8)	FACT-C FACT-B FACT-BI FACT-P	36	0-136	Δ5-8 ~clinically significant Reported based on the past 7 days

*For each metric, we will test for internal consistency ratings across the three assessment time points (T0, T1, and T2).

Healthcare utilization. All patients in the intervention and control arms at the time of T0, T1, and T2 assessments will be asked about their healthcare utilization since the last assessment including primary care, specialist and ED visits and any hospital stays. This information will be validated with the patient SO and medical record/PCP. We will also ask about reasons for the visits to further distinguish utilization into avoidable (consequence of poor quality of care or insufficient self-management skills) and unavoidable (true healthcare emergency).

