25.0 Provisions to Protect the Privacy Interests of Subjects

Only study coordinators and RAs will know the identity of the patients. Once the data are collected (from patient EHR and study instruments) and inputted into REDCap database, each patients will be referred to only by their study ID. The study participation can be discontinued at any time and patients may decline to answer any questions they find upsetting.

The subjects will be initially approached by their clinic staff to inform them about the study. Only subjects who expressed interest in the study will be then contacted by the study team. All members of the subject's clinical team will receive information about the study and will be qualified to discuss with the study subjects their questions/concerns. The study participation can be discontinued at any time and patients may decline to answer any questions they find upsetting. The study RAs are certified therapists and are qualified to handle patient distress or refer them to mental health providers as appropriate.

Only study coordinators and RAs will be allowed to access information about the subjects in the EHR system for the purpose of confirming subject eligibility, abstracting their medical history and scheduling the first meeting with the therapist. The de-identified study data will be accessed only from a UB or Roswell Park secure password protected computer by pre-identified and appropriately trained faculty and staff.

Roswell Park Protocol Number. I 65518

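### Outside RPCI the described record check confirms only visits the patient has reported; no step is given for finding unreported visits, so undercounting is possible and ascertainment differs by site.

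*Combined protocol and SAP*

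**What the plan says.** Utilization is collected by self-report. Under Section 11.0, patients in both arms, at T0, T1 and T2, "will be asked about their healthcare utilization since the last assessment including primary care, specialist and ED visits and any hospital stays".

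A general validation rule follows, with no site distinction: "This information will be validated with the patient SO and medical record/Primary Care Provider (PCP) office staff". Section 8.0 repeats it almost unchanged: "This information will be validated with the patient SO and medical record/PCP".

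Section 11.0 then describes how the record check is done, in two forms:

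- RPCI: "For RPCI patients, information about number and timing of care visits will be requested electronically".
- External patients: "the RA will call the PCP office staff and confirm all patient-reported clinic visits after the medical record release form is signed".

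The term for external patients is not defined. The natural reading is everyone not treated at RPCI, that is, patients at WCI and at NMH, its rural affiliate.

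Three other places bear on the point. Section 25.0 allows study coordinators and RAs into the EHR "for the purpose of confirming subject eligibility, abstracting their medical history and scheduling the first meeting with the therapist"; utilization is not listed. H4 in Section 1.0 sets the expectation for supportive others: "At least 50% of patients with cancer will identify a significant other to join them in PSST training". Section 19.0 says utilization will be compared between arms with Poisson and negative binomial models, for trend only.

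**The concern.** The two checks are not equivalent. A request for the number and timing of visits produces a list that does not depend on the patient's memory, so it can show both over-reporting and omission. A call that works through the patient's own list can show only over-reporting. It is also worded for clinic visits, while the outcome includes specialist and ED visits and hospital stays.

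Two things are at stake. First, absolute utilization rates, and any comparison of rates between sites, may reflect how visits were found as well as how often patients sought care. That matters because the results are meant to inform a larger multisite trial. Second, if patients in one arm remember more of their visits than patients in the other, the ratio between arms is distorted wherever omissions are not recovered. Patients cannot be blinded to a therapy of eight one-hour sessions. Care coordination is among the problems listed in Table 1 for discussion, and supportive others are invited to the sessions. A difference in recall is therefore conceivable.

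**Working it through.** The plan states no omission rate, target or precision for utilization, so there is no figure of its own to reproduce. The check has two parts: what each route can detect, and how far an undercount would carry.

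**1. What each described route can detect outside RPCI**

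| Route | Removes over-reports | Finds omitted visits |
|---|---|---|
| Call to PCP office (11.0) | Yes, for clinic visits | No step described |
| Medical record (8.0, 11.0) | Possible | Possible, but no procedure is given and Section 25.0 does not list this use of the EHR |
| Supportive other (8.0, 11.0) | Possible | Possible, where there is one; H4 requires only 50%, so up to half of patients may have none |

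**2. Share of patients concerned**

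Section 4.0 expects "3 new survivors a month at Wilmot Cancer Institute (WCI), 2 from RPCI (up to 20), and 1 new survivor every other month" at NMH, for 10 months, stopping at 50.

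- Expected over 10 months: WCI 3 × 10 = 30; RPCI 2 × 10 = 20; NMH 0.5 × 10 = 5; total 55.
- Pro rata: (30 + 5)/55 = 63.6%, or about 32 of 50.
- If RPCI reaches its cap of 20 and enrolment stops at 50: 30/50 = 60%.

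**3. Size of an undercount**

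Let *e* be the external share (0.600 or 0.636) and *u* the proportion of visits that external patients omit. Assumptions, none from the documents: *u* between 5% and 30%; nothing recovered through the supportive other or the record; complete capture at RPCI; the same visit rate per patient at every site.

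- Pooled undercount = *e* × *u*. Example: 0.600 × 0.20 = 12.0%; 0.636 × 0.20 = 12.7%.
- Apparent rate ratio, PSST to CAU, when the true ratio is 1 and omission is equal in both arms: (1 − *eu*)/(1 − *eu*) = 1.00, since allocation is 1:1 within site (Section 9.0).
- Apparent rate ratio if PSST patients omit half as much as CAU patients: (1 − *eu*/2)/(1 − *eu*). Example: (1 − 0.06)/(1 − 0.12) = 0.94/0.88 = 1.068.

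| Assumed *u* (CAU) | Pooled count low by, equal omission | Ratio, equal omission | Ratio if PSST omits *u*/2 |
|---|---|---|---|
| 5% | 3.0–3.2% | 1.00 | 1.015–1.016 |
| 10% | 6.0–6.4% | 1.00 | 1.032–1.034 |
| 20% | 12.0–12.7% | 1.00 | 1.068–1.073 |
| 30% | 18.0–19.1% | 1.00 | 1.110–1.118 |

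The last column is illustrative in direction as well as size. With the roles reversed (PSST omits 20%, CAU 10%) and *e* = 0.600, the ratio is 0.88/0.94 = 0.94.

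**4. Against the precision of the comparison**

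Assume 25 patients per arm, a mean of 5 visits each and Poisson variation (the mean is an assumption). Each arm then has 125 visits, and the standard error of the log rate ratio is √(2/125) = 0.126. An observed ratio of 1.07 would have a 95% interval of about 0.84 to 1.37, wider still with overdispersion.

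**The case against.** The strongest reply is that the protocol does not rest on the call alone. The validation rule covers every patient and names both the supportive other and the medical record, and inclusion criterion 5 secures access to records and PCP for all participants. Either source could reveal a forgotten visit. This stands. A reader might infer from the wording of the call that forgotten visits are never found and that counts outside RPCI are too low. The documents support neither statement: other routes are named, and no omission rate is given. What remains is that those routes have no procedure for finding unreported visits outside RPCI.

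Second, RPCI may not be a complete comparator. Section 11.0 does not say whether the electronic request reaches care delivered elsewhere. This also stands. The finding is that ascertainment differs by site, not that one site's is complete.

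Third, randomization is stratified by site, so a site difference falls equally on both arms. That is correct when recall is equal in both arms. A reader might go further and infer a bias towards more use under PSST. The documents contain nothing on recall by arm, so neither the direction nor the size of such a bias can be claimed.

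Fourth, utilization is in none of H1 to H5 and its models are for trend only. True, and the interval above shows that a shift of 7% would be lost in the noise of this study. That limits the weight of the point, but it does not make a one-directional check preferable to a two-directional one that uses the same call.

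**Conclusion.** The point holds as a gap in the described procedure. For external patients, Section 11.0 states a check that can remove visits but has no stated step to add them, while RPCI visits are requested independently of patient report. On the natural reading of external, this concerns about 60–64% of planned patients. Undercounting is possible, its size is unknown, and ascertainment differs by site. The 3% to 19% range for the pooled count depends wholly on the assumptions listed with it.

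Absolute rates and site comparisons are exposed even when recall is equal in both arms. The arm comparison is exposed only if recall differs by arm, which is possible in an unblinded intervention but is not shown. Because utilization is a secondary, trend-only measure, this is a low-cost improvement to data capture and does not threaten the study's main hypotheses.

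**What to change.** Amend Section 11.0 as follows:

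- Define external patients.
- In the call already planned, under the release form already planned, ask the PCP office for all visits and dates in the assessment window, including any ED, specialist or hospital care on file, before disclosing what the patient reported.
- State what the RPCI electronic request covers, and make it for the same window and visit types.
- Apply one reconciliation rule at every site. Add visits found only in the record. Keep visits reported only by the patient, but flag them as unconfirmed. Report a sensitivity count that drops flagged visits which the source should have held, such as a visit to that PCP's own office.

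The last rule preserves the check on over-reporting, which a plain union of the two sources would give up. If the sites' own EHRs are to be used for this purpose, Section 25.0 should list it.

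The cost is a few sentences of text, slightly longer calls and a source flag for each visit in the database. PCP records may still miss some outside care, so the change reduces the gap without closing it.

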12.0 Withdrawal of Subjects

As long as the subjects are willing and able to participate in the study, they will be kept in the study and followed as planned.

13.0 Risks to Subjects

We are unaware of any potential risks from participation and have seen no reports of adverse effects during the prior PSST projects (total n=900 subjects). All records will be kept strictly confidential as required by the policies and procedures of the participating institutions. Should a subject become distressed while completing a questionnaire or participating in an intervention

Roswell Park Protocol Number. I 65518

session to an extent that exceeds the research assistant's clinical experience, the issue will be discussed with the site PI or the subject will be referred to a mental health professional as appropriate. Provision of 1 hour of supervision for each four hours of subject contact and review of a sample of audiotapes from therapy sessions by [name], experienced licensed health professional, adds another layer of monitoring to ensure subject safety.

